### 4.2 Handling of dropouts or missing data

#### 4.2.1 Handling of missing data for efficacy variables

Based on previous studies of biologics in subjects with moderate to severe chronic plaque psoriasis, it is expected that the number of subjects who discontinue prior to Week 16 will be low. For the small percentage of subjects for whom primary endpoint data are unavailable at Week 16, this lack of data is suggestive of an ineffective study treatment, thereby supporting the imputation of nonresponse. Achieving the clinical response and making it through 16 weeks of study treatment are both critical components of the primary outcome. Therefore, non-responder imputation (NRI) is considered an appropriate method for handling missing data.

If a subject discontinues early from the study, all efficacy data that are collected later than 35 days after the last administration of study treatment will be treated as missing and subject to imputation as applicable.

Study variables with multiple components may have rules to account for partial missing data of 1 or more components. Such rules will be defined in section 8 for applicable endpoints. The following rules are outlined for cases where variables are completely missing, including partial missing data where the data handling rules conclude that the variable should be treated as completely missing.

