#### **4.2.1.3 Handling missing data for the other efficacy variables**

For other binary efficacy variables, missing data will be imputed using NRI as primary method.

For other continuous efficacy variables, multiple imputation (MI) will be used to impute missing data when possible. If the imputation model cannot converge, last observation carried forward (LOCF) will be used. The MI procedure will be similar to sensitivity analysis #1 described in Section 8.1.3.1 with the following differences:

1. No dichotomization will be necessary.
2. Instead of using the stratified Cochran-Mantel-Haenszel (CMH) test, the imputed data sets will be combined, and simple means and standard errors will be calculated using Rubin's rules (via SAS PROC MIANALYZE). For calculation of other descriptive statistics such as the median, minimum and maximum, Rubin's rules do not apply. Multiple imputation estimates will be computed by simply averaging the estimates from the multiple repetitions of the imputation algorithm.

For other ordinal variables (IGA score, EQ-5D-3L and Patient Global Assessment of PSO), OC method will be applied as the primary analysis method. No imputation is applied.

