#### 4.2.1.5 Missing data overview and summary

In summary, the approaches listed below will be used in this study for handling missing data for efficacy variables as appropriate:

- NRI: Subjects who have missing data at the time point of interest are treated as though they did not respond to the treatment.
- MI –MCMC / Monotone Regression: Using multiple imputation methodology, intermittent missing data are imputed based on the MCMC method, and monotone missing data are imputed using monotone regression. Note: for all analyses and summaries using MI, subjects with missing baseline value will be excluded.
- LOCF: Post-Baseline missing data are imputed by carrying forward the last available observation (including Baseline).
- OC: Missing data are not imputed. Only subjects with available data who have not discontinued study treatment at the given time point are considered.

The following table depicts which missing data handling approaches should be used based on variable priority (primary, secondary, other) and variable type (responder, continuous, ordinal).

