**Table 4–1: Missing data handling approach by variable priority and type**

Variable Priority	Variable Type	NRI	MI (MCMC/ Monotone Regression)	LOCF	OC
Primary	Responder	P	S a	S	S
Secondary	Responder	P	S a	B	S
Other	Responder	P			S b,c
	Continuous e		P	B	
	Ordinal				P d

P=Primary method, S=Sensitivity method, B=Backup method, NRI=Nonresponder imputation, MI=Multiple imputation, MCMC=Markov Chain Monte Carlo, LOCF=Last observation carried forward, OC=Observed Case  
Note: Backup method is only applicable when the primary/secondary method is unable to converge due to challenges with the imputation model.

Note: Additional missing data handling approaches are detailed in Section 4.2.1.7 for assessing the impact of COVID-19 on the secondary efficacy variable PASI100 response at Week 48.

a Imputation method is applied on continuous data, and responder variable is derived from the continuous variable based on complete data set.

b Only applies to by-visit summaries of variables that are in the multiplicity-controlled testing procedure.

c Includes IGA Responses, PASI75, PASI90 and PASI100.

d Includes IGA score, Patient Global Assessment of PSO and EQ-5D-3L.

e For PASE, OC is the primary analysis method.

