**Table 4-2: Allowable ranges for imputation by variable**

Variable	Minimum value	Maximum value	Integer values only
PASI	0	72	No
IGA	0	4	Yes
PSD items (itch, pain, scaling)	0	10	No
Scalp IGA	0	4	Yes
mNAPSI	0	130	No
BSA	0	100	No
IGAxBSA	0	400	No
DLQI	0	30	Yes
PGADA	0	100	No
EQ-5D-3L VAS	0	100	Yes

Variable	Minimum value	Maximum value	Integer values only
WPAI dimension scores	0	100	No for variables: “Percent work time missed due to problem” and “Percent overall work impairment due to problem”. Yes for variables: “Percent impairment while working due to problem” and “Percent activity impairment due to problem”. These two variables can only take values that are multiples of 10.
PHQ-9	0	27	Yes

- The Week 16 results from the specified statistical analysis (e.g. stratified CMH, logistic regression) of each of the 100 imputed data sets will be combined for overall inference using Rubin’s rules, which account for the uncertainty associated with the imputed values (Rubin, 1987). This will be done using SAS PROC MIANALYZE.

Some key points to consider relative to the calculation of the odds ratios and corresponding confidence intervals are noted below:

If stratified CMH or logistic regression are used, the estimates of the odds ratios from the logistic regression model in step 3 follow a log-normal distribution, and a log transformation is needed to normalize these estimates since the procedures for combining results from multiple imputed datasets are based on the assumption that the statistics estimated from each imputed dataset are normally distributed. Therefore, the log of the odds ratio estimates from the logistic regression model are used when combining into a single inference (the use of PROC MIANALYZE in step 3). Appropriate transformations to the standard errors and p-values should also be made in order to get the correct confidence intervals, for the CMH test using the p-value for the general association the Wilson-Hilferty transformation should be used (Ratitch, 2013).

For other continuous efficacy variables, MI will be used to impute missing data when possible (see Section 4.2.1.3). If the imputation model cannot converge, LOCF will be used.

Further details about imputation for different analysis sets are below:

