### **8.3.12 Work Productivity and Activity Impairment Questionnaire – Specific Health Problem (WPAI-SHP)**

The WPAI-SHP is a subject-reported questionnaire that assesses subject's employment status, work absenteeism, work impairment while working, overall work, and daily activity impairment attributable to a specific health problem. Five out of 6 items of the WPAI-SHP are regrouped into the 4 dimensions, with scores expressed as percentage, where higher numbers indicate greater impairment and less productivity, i.e., worse outcomes, as described in the WPAI-SHP scoring rules.

The scoring rules for the WPAI-SHP are as follows:

Questions:

- 1 = currently employed
- 2 = hours missed due to specified problem
- 3 = hours missed other reasons
- 4 = hours actually worked
- 5 = degree problem affected productivity while working
- 6 = degree problem affected regular activities

Scores:

- Percent work time missed due to problem:  $[Q2 \text{ hours}/(Q2 \text{ hours} + Q4 \text{ hours})]*100$
- Percent impairment while working due to problem:  $[Q5 \text{ score}/10]*100$
- Percent overall work impairment due to problem:  
 $[Q2 \text{ hours}/(Q2 \text{ hours} + Q4 \text{ hours}) + [(1 - (Q2 \text{ hours}/(Q2 \text{ hours} + Q4 \text{ hours})) \times (Q5 \text{ score}/10)] ] *100$
- Percent activity impairment due to problem:  $[Q6 \text{ score}/10]*100$

Change from Baseline score is derived as post Baseline score minus Baseline score. A negative change score indicates a reduction in the score/improvement for the subject.

The Change from Baseline in WPAI-SHP will be summarized for each study period (Initial randomized, Maintenance) by treatment group and for OLE by treatment sequence at each visit.

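### For subjects with a Baseline work score who are not employed at a later visit, the SAP's multiple-imputation rule generates three WPAI work scores that do not exist, because not applicable is not separated from missing

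*SAP*

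**What the plan says.** - Section 4.2.1.3 gives the general rule for this class of variable: "For other continuous efficacy variables, multiple imputation (MI) will be used to impute missing data when possible". LOCF replaces MI if the imputation model does not converge.
- Table 4-1 repeats MI as primary and LOCF as backup for other continuous variables. Its footnote makes one exception: "For PASE, OC is the primary analysis method". WPAI is not excepted.
- Table 4-2 lists "WPAI dimension scores" with an allowed range of 0 to 100 and names all four scores. Of impairment while working and activity impairment it says: "These two variables can only take values that are multiples of 10".
- Section 4.2.1.5 states one exclusion: "for all analyses and summaries using MI, subjects with missing baseline value will be excluded".
- Section 4.2.1 defers handling of partly missing components: "Such rules will be defined in section 8 for applicable endpoints".
- Section 8.3.12 lists employment as the first question ("1 = currently employed") but uses it in none of the four score formulas and in no restriction of the analysis set. It then says: "The Change from Baseline in WPAI-SHP will be summarized for each study period (Initial randomized, Maintenance) by treatment group", and extends this to the OLE by treatment sequence.

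**The concern.** Three of the four WPAI scores describe a person's work: time missed, impairment while working, and the combination of the two. For someone without a job at the visit there is no unobserved true value to recover. Section 4.2.1.6 justifies MI on the ground that values lost after treatment discontinuation are missing at random. That argument does not cover a quantity that is undefined.

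The SAP makes this kind of distinction elsewhere. DLQI scoring (Section 8.3.5) treats an answer of not relevant differently from an unanswered item. The scalp and palmoplantar IGA analyses (Section 8.3.2) are limited to subjects in whom a response is attainable. WPAI applicability can change from visit to visit, yet it has no comparable rule.

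At stake are the reported mean changes in work impairment, their standard errors and their n. These would combine observed scores with values generated for people who are not working. Departure from work, itself an outcome of interest for a work-productivity objective (Section 2.1.3), would not be visible in the tables. Two programmers could also reasonably differ on whether to impute.

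**Working it through.** The SAP contains no figure on this point to reproduce, so the check is mainly a reading of its rules in sequence, followed by an illustration of size.

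**Step 1: which scores need employment.** From the formulas in Section 8.3.12, with Q2 = hours missed because of the problem, Q4 = hours worked, Q5 = effect on productivity while working and Q6 = effect on regular activities:
- Work time missed = 100 × Q2/(Q2+Q4). Undefined when Q2+Q4 = 0.
- Impairment while working = 100 × Q5/10. Has no meaning when no hours were worked (Q4 = 0).
- Overall work impairment = 100 × [Q2/(Q2+Q4) + (1 − Q2/(Q2+Q4)) × Q5/10]. Undefined when Q2+Q4 = 0.
- Activity impairment = 100 × Q6/10. Does not depend on employment.

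Three scores are affected and one is not.

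**Step 2: follow each type of subject through the rules.**
- *Not employed at Baseline.* There is no Baseline work score, so Section 4.2.1.5 excludes the subject from the MI summaries. No value is created.
- *Employed at Baseline, not employed at a later visit.* A Baseline score exists, so the exclusion does not apply. The later score is absent, Table 4-1 gives no exception, and Section 8.3.12 gives no rule. Under Section 4.2.1.6 a gap with data before and after is filled by MCMC, and a gap with nothing after it by monotone regression. Under the LOCF backup, a score from a period of work is carried into a period without work.
- *Questionnaire absent, or set to missing by the 35-day rule in Section 4.2.1.* Employment at that visit is unknown. This is ordinary missingness, and MI is a reasonable choice.

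Only the second group is the problem.

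**Step 3: illustrative size, double-blind visits only.** Inputs: 350 per randomised arm (Section 2.4). Assumptions, not in the SAP: a share e = 50% to 80% employed at Baseline, and a share q = 2% to 10% of those not employed at a given later visit.

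Subjects per arm with a Baseline score = 350 × e; excluded = 350 × (1 − e); affected at the visit = 350 × e × q.

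| e | Excluded at Baseline | In the summary | Affected, q = 2% | q = 5% | q = 10% |
|---|---|---|---|---|---|
| 50% | 175 | 175 | 3.5 | 8.8 | 17.5 |
| 60% | 140 | 210 | 4.2 | 10.5 | 21.0 |
| 70% | 105 | 245 | 4.9 | 12.2 | 24.5 |
| 80% | 70 | 280 | 5.6 | 14.0 | 28.0 |

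That is about 4 to 28 subjects per arm, or 2% to 10% of those summarised. This is the share of values generated for non-workers; it is not an estimate of bias in a mean. The count applies to the two randomised arms and does not carry over to the maintenance groups or the OLE sequences, which have other denominators.

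**The case against.** The strongest case against has four parts.

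- **The SAP nowhere orders imputation for people without a job.** Section 4.2.1.3 imputes missing data when possible, and Section 8.3.12 refers to the instrument's own scoring rules, which may settle who has a score. It is true that there is no express instruction. But those rules would at most leave the score blank, and a blank score in a variable named in Table 4-2 falls under MI unless the SAP says otherwise. It does not.
- **Most non-workers may already be excluded.** A reader might infer that scores are imputed for everyone not employed at a visit. Section 4.2.1.5 rules that out for anyone without a Baseline work score. This part stands and limits the point to those who leave work after Baseline.
- **The imputation is not naive.** A reader might infer that someone who left work because of severe disease is given an average worker's score. Section 4.2.1.6 uses the subject's own Baseline and earlier visit values as predictors, separately by treatment group, so earlier severe impairment informs the imputed value. This also stands: the direction of any distortion cannot be stated. It does not give meaning to a value that is undefined.
- **Leaving these visits out also hides work loss.** A summary restricted to the employed conditions on a post-randomisation state and, by itself, shows departures from work no better. This is right, and it is why employment counts must be part of the remedy.

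**Conclusion.** The point holds in a limited form. Following the SAP as written, the three work scores are filled in at visits where a subject with a Baseline score is not employed. This follows from a stated general rule combined with the lack of a not-applicable category in Sections 4.2.1 and 8.3.12.

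The consequence is small. WPAI is an other efficacy variable, outside the fixed testing sequence of Section 4.5 and absent from the nominal tests of Section 8.4. A reader might infer a threat to a confirmatory conclusion; there is none. What is affected is the descriptive mean, standard error and n of three scores.

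The 2% to 10% share rests wholly on assumed employment figures, and no effect on a mean or on a treatment difference has been shown. It may be tempting to project a larger count to Week 144. The documents do not support that: the OLE is optional, its analysis set is the OLS, and results are given by treatment sequence, so 350 per arm is not the denominator. The change is still worth making because it is specific and cheap and keeps undefined values out of reported results.

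**What to change.** In Sections 8.3.12 and 4.2.1.3, state that:

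1. Where the subject answers no to current employment at a visit, the three work scores are not applicable. They are left out of that visit's summary and not filled by MI or LOCF; any value the MI procedure generates there is discarded before summarising.
2. The same applies to impairment while working when Q4 = 0, and to work time missed and overall work impairment when Q2+Q4 = 0.
3. MI remains in use where the questionnaire is absent or set to missing and employment at the visit is therefore unknown.
4. The number employed, and the number who have left employment since Baseline, are reported by visit and treatment group so that work loss is visible.

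Activity impairment needs no change. The cost is a short addition to the SAP and a rerun of the WPAI tables. The n becomes slightly smaller, and the work-score summaries become conditional on employment after randomisation, which a table footnote should say.

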#### **4.2.1.4 Handling missing data for subgroup analyses**

For subgroup analyses specified in Section 4.8, NRI will be used for responder variables. Only descriptive statistics will be provided.

#### 4.2.1.5 Missing data overview and summary

In summary, the approaches listed below will be used in this study for handling missing data for efficacy variables as appropriate:

- NRI: Subjects who have missing data at the time point of interest are treated as though they did not respond to the treatment.
- MI –MCMC / Monotone Regression: Using multiple imputation methodology, intermittent missing data are imputed based on the MCMC method, and monotone missing data are imputed using monotone regression. Note: for all analyses and summaries using MI, subjects with missing baseline value will be excluded.
- LOCF: Post-Baseline missing data are imputed by carrying forward the last available observation (including Baseline).
- OC: Missing data are not imputed. Only subjects with available data who have not discontinued study treatment at the given time point are considered.

The following table depicts which missing data handling approaches should be used based on variable priority (primary, secondary, other) and variable type (responder, continuous, ordinal).

**Table 4–1: Missing data handling approach by variable priority and type**

Variable Priority	Variable Type	NRI	MI (MCMC/ Monotone Regression)	LOCF	OC
Primary	Responder	P	S a	S	S
Secondary	Responder	P	S a	B	S
Other	Responder	P			S b,c
	Continuous e		P	B	
	Ordinal				P d

P=Primary method, S=Sensitivity method, B=Backup method, NRI=Nonresponder imputation, MI=Multiple imputation, MCMC=Markov Chain Monte Carlo, LOCF=Last observation carried forward, OC=Observed Case  
Note: Backup method is only applicable when the primary/secondary method is unable to converge due to challenges with the imputation model.

Note: Additional missing data handling approaches are detailed in Section 4.2.1.7 for assessing the impact of COVID-19 on the secondary efficacy variable PASI100 response at Week 48.

a Imputation method is applied on continuous data, and responder variable is derived from the continuous variable based on complete data set.

b Only applies to by-visit summaries of variables that are in the multiplicity-controlled testing procedure.

c Includes IGA Responses, PASI75, PASI90 and PASI100.

d Includes IGA score, Patient Global Assessment of PSO and EQ-5D-3L.

e For PASE, OC is the primary analysis method.

#### 4.2.1.6 Missing data algorithm – MI – MCMC / Monotone Regression

Investigators will be given discretion to discontinue study treatment for subjects not responding in order to provide them with alternative therapy to treat the condition. Therefore, in many cases, missing efficacy data due to study treatment discontinuation should be dependent on the observed efficacy scores, but independent of unobserved data. This would be consistent with a

missing at random (MAR) pattern of missingness. To investigate the efficacy results under the assumption of data being MAR, a multiple imputation method will be applied as follows (exemplary for PASI100 at Week 16):

1. Create a data set, one for each treatment group (note that a separate imputation procedure must be invoked in SAS for each treatment group as the seed cannot be set for by groups beyond the first when using a by statement, see notes below about treatment groups to use for different analysis sets), of subjects with observed values and those needing estimation by multiple imputation. The intermittent missing PASI/IGA values in each data set (i.e., missing values for a given subject that has available data before and after the missing time point) will be filled in using the MCMC method, with a total of 100 sets of imputations being performed. The seed used for these imputations will be 852 (note that all other multiple imputation procedures described in this SAP related to MCMC/Monotone Regression analyses will use this same seed as well). For monotone missing data (i.e., where all subject data is missing after a given time point), monotone regression will be used to impute missing data. Again, this will be based on the 100 sets of imputations already created using the MCMC method such that there will be 100 imputations in total. In both cases, biologic exposure, geographic region and PASI/IGA values at Baseline and at each post-Baseline visit (in chronological order, see notes below about visits to include for different analysis sets) will be included in the imputation model. Note that PASI scores at earlier visits will also be used as predictors for the model of PASI at later visits. The resulting data sets for each treatment arm will be combined into one complete data set based on each of the 100 imputations.

Note: The imputation model will only allow continuous variables. Therefore, prior biologic exposure and region will be re-coded as indicator variables. For prior biologic exposure, this will simply be 0 for biologic-naïve subjects and 1 for biologic-exposed subjects. For region, which has 4 levels, one indicator variable will be defined as 0 for regions other than North America and 1 for North America. Two more indicator variables will be defined similarly replacing North America with Central/Eastern Europe, and Western Europe respectively. An indicator variable for Asia/Australia is not needed as the fourth region will be adequately represented by the other region indicator variables all being 0. In the event that the percentage of randomized subjects is less than 10% in either of the Asia/Australia or Western Europe region, the two regions will be combined as a geographic region stratum for efficacy modeling, so that there are no modeling convergence issues across efficacy variables. In order to achieve model convergence, prior biologic exposure may be dropped from the model. If convergence is still not obtained, then region may also be dropped from the model.

2. For each complete imputed data set, the dichotomous responder variable (PASI100) based on the PASI scores will be computed. Each complete imputed data set will then be analyzed based on the stratified CMH test.

Note: For derivation of PASI100 response, the PASI value at Week 16 in the imputed data sets will be compared directly to the observed Baseline PASI value to determine whether or not a reduction of 100% was achieved. If values outside of the pre-defined

range of values for PASI (0-72) are imputed, they will be cut off as appropriate after the multiple imputation procedure but before deriving the responder variable. For example, an imputed PASI value of -0.5 would be changed to 0 before deriving the PASI100 responder variable.

Note: Standard rounding rules will be applied to the imputed IGA values in order to derive the binary IGA 0/1 responder variable. In addition, if values outside of the pre-defined range of values for IGA (0-4) are imputed, they will be cut off as appropriate after the multiple imputation procedure but before deriving the responder variable. For example, if a subject has an IGA score imputed as 1.4 (and assuming a Baseline IGA score of 3), this imputed value would be rounded down to 1, and the minimum change from Baseline of 2 would have been met. Therefore, this subject would be considered an IGA 0/1 responder.

Additional ranges of values for other variables are defined in [Table 4-2](#).

